4.4.2 Secondary endpoints

The analysis of the following parameters is defined as secondary endpoints

III. Secondary endpoints t1-t3

- 1) Vital parameter and lung function parameters
 - a. height, weight, oxygen saturation
 - b. forced expiratory spirometry (PEF, FEV1, FVC, MEF)
- 2) Laboratory parameters
 - a. full blood analysis (blood sampling from the vein) 4

IV. Secondary endpoints t1-t4

- 1) Resilience (questionnaires)
 - a. State-Trait-Assessment of Resilience Scale (STARS), (Lock et al., 2020), German version

⁴ A total of 25 ml of blood is taken.

- b. Perceived Stress Scale, German version (Cohen et al., 1983; Schneider et al., 2020)
- c. Brief Sense of coherence scale (SOC-3) (Schumann et al., 2003)
- 2) Mindfulness (questionnaires)
 - a. Five Facet Mindfulness Questionnaire (FFMQ-15) (Baer et al., 2012), German version
- 3) Physical activity (Questionnaire)
 - a. International Physical Activity Questionnaire Short Form (IPAQ-SF), German version (IPAQ, 2019)
- 4) Nature contact (questionnaires)
 - Nature connectedness (Inclusion of Nature in Self Scale (INS), German version, (C. Martin & Czellar, 2016; adapted from P. W. Schultz, 2002) and Nature Connectedness Index (NCI)
 - b. Direct nature contact (People and Nature Survey 2023, M1-Q1, (Marshall, 2023)
 - c. Indirect nature contact (Gu et al., 2023; adapted from L. Martin et al., 2020)
- 5) Subjective well-being and quality of life (questionnaires)
 - a. Intercultural Quality of Life Comic (Pichler, 2020)
 - b. OECD-4 (OECD, 2013)
- 6) Social aspects (questionnaires)
 - a. Loneliness: German short version of the De Jong Gierveld Loneliness Scale (Gierveld & Tilburg, 2006)
 - b. Community cohesion: German short version of the Community Cohesion Scale, (Weinstein et al., 2015)
- 7) Motivation (questionnaires)
 - a. Ideal self, based on (Ganesan, 2020)
 - b. Self-determined motivation (Astell-Burt et al., 2024)

V. Integrative evaluation parameters (t1-t4)

- 1) Environmental aspects (t1-t4):
 - a. (Perception of local nature, PANS-6, People & Nature Survey 2023 (Marshall, 2023))
 - b. Environmental concerns adapted from (W. Schultz, 2001)
 - c. Pro-Environmental Behavior, Revised Pro-Environmental Behavior Scale (R-PEBS), adapted in consultation with the author (Brick et al., 2017)
- 2) Health economic aspects (t1-t4)
 - a. Quality Adjusted Life Years (QUALY): calculation from SF-12

- b. Use of Care Services (cost savings)
- c. Willingness to pay via Contingent Valuation Method (CVM)
- 3) Process evaluation (t1-t4)

The following parameters are collected from the study participants for process evaluation:

- a. Satisfaction with the intervention
- b. Willingness to repeat
- c. Willingness to recommend

In addition, qualitative interviews are conducted with study participants and members of the study team for process evaluation after the intervention. The questions used for the interviews are included in the appendix.

4.5 Study timeline

Participation in the clinical study involves four measurement time points over a period of 180 days:

- **T1 (day 1):** Baseline data assessment directly before the intervention for intervention and control group; data assessment at the premises of the Paracelsus Medical University Salzburg
- **T2 (day 35):** data assessment after the onboarding (week 1) and integration phase (week 2-5) for all study participants of the intervention and control group at the premises of the Paracelsus Medical University Salzburg
- **T3 (day 70):** data assessment for all study participants of the intervention and control group after the first follow-up phase (week 6-10) at the premises of the Paracelsus Medical University Salzburg
- **T4 (Tag 180):** data assessment for all study participants of the intervention and control group after the first follow-up phase (week 6-10) via online questionnaire

[figure not shown]

Figure 1: Study timeline

The present clinical study is planned in two rounds:

- Round 1: from September 2024: intervention group, waiting list control group
- Round 2: ab March 2025: intervention group, waiting list control group

The implementation in two rounds results from the capacities of the study team (hiking guides, therapists).

For ethical reasons, the control group is designed according to the principle of a waiting list control group (Elliott & Brown, 2002). This implies that the individuals in the control group will also have the chance to benefit from the nature-based therapy. The offer will be made to the control group after all measurements have been completed (after t4) in spring and fall 2025.

The allocation of groups is random.

4.6 Sample size

The calculation of the sample size is based on published study results from the Institute of Ecomedicine. The study investigated the effect of nature-based therapy on individuals with sedentary lifestyles. (Huber et al., 2023; Pichler et al., 2022, ISRCTN43292449 https://doi.org/10.1186/ISRCTN43292449):

- Study type: two-armed randomized controlled clinical trial
- Intervention: nature-based therapy (mindfulness-based forest therapy vs. hiking; Forest vs. Hiking)
- Outcome parameter for sample size calculation: health-related quality of life (SF-12)
- Study population: 50-60 years, sedentary lifestyle, moderate overweight (BMI ≥25–≤30)

The sample size was calculated with a bootstrap simulation (using the software R-GNU, Genal Public License, R Foundation for Computing), applying the F1-LD-F1 model from the nparLD package (Nonparametric Longitudinal Data Analysis) (Noguchi et al., 2012). The initial seed for the variate generator was set at 1 and the re-sampling process was fixed to 1000 repetitions for each sample size. The percentage of significant results was used as an estimator of power.

Regarding clinical studies on lifestyle interventions in overweight individuals, recent literature reports dropout rates ranging from 30% to 50% (Collins et al., 2022; Ruelas et al., 2023).

A drop-out and lost-to-follow-up rate (until T4 = day 180) of 40 % was assumed for the present study, resulting in a sample **size of n=70 per study arm**.

Sample size	Туре	FALSE	TRUE	Power	Comparison
10	nparLD	698	302	0,302	FoHi
20	nparLD	485	515	0,515	FoHi
30	nparLD	316	684	0,684	FoHi
40	nparLD	183	817	0,817	FoHi
50	nparLD	127	873	0,873	FoHi
60	nparLD	58	942	0,942	FoHi
70	nparLD	38	962	0,962	FoHi
80	nparLD	18	982	0,982	FoHi
90	nparLD	11	989	0,989	FoHi
100	nparLD	3	997	0,997	FoHi

Table 1: Sample size calculation based on Huber et al., 2023

FoHi = Forest vs. Hiking

[figure not shown]

Figure 2: Sample size calculation based on Huber et al., 2023

4.7 Recruitment

The clinical study will recruit a total of 140 participants, with 70 in each study arm. The University Clinic for Internal Medicine I of the Salzburg University Hospital (study center 2) will conduct clinical inclusion, while the Institute for Ecomedicine of the Paracelsus Medical University Salzburg (study center 1) will carry out the intervention.

Study participants can register for the study through the Paracelsus Medical University website (primary source, www.pmu.ac.at/ecomedicine).

A total of 140 study participants are recruited through the following channels:

1) Paracelsus 10,000 data base

People with metabolic syndrome aged between 40 and 65 years will be identified from the database of the Paracelsus 10,000 Study(Frey et al., 2021). A sample of n=500 people, stratified by age and sex, will then be selected from these data and informed by post about the possibility of participating in the study.

2) University clinic for internal medicine I of the Salzburg University Hospital

In addition, recruitment will take place via the outpatient clinics (metabolic, diabetes, obesity) of the University Clinic for Internal Medicine I of the University Hospital Salzburg (head physician: Univ. [name]. [name]; active approach of eligible persons, website, distribution of information material).

3) Resident general practitioners and internists

Information material about the study will be sent to local internists and general practitioners (GPs) in the city of Salzburg and surrounding communities to make eligible patients aware of the opportunity to participate in the study.

The design and content of the digital and analog advertising material are identical.

The communication of the clinical study and the recruitment of study participants will be carried out in compliance with the guidelines for advertising study participation of the Ethics Commission of the Federal State of Salzburg.

An online questionnaire will be used for enrolment and an initial assessment of the inclusion and exclusion criteria. The data collected during registration will be stored on a secure server at the Paracelsus Medical University of Salzburg and will only be used to contact participants and assess their eligibility. The data will be deleted after recruitment is completed.

4.8 Informed consent

Participants will be informed in writing (informed consent) and verbally about the study, the required examinations and potential risks before the study begins. To be included in the study, the participant must sign an informed consent form. The inclusion and exclusion criteria and the informed consent will be sent to participants in advance and will be reviewed at the inclusion visit (t1). As part of the informed consent process, participants are also informed that refusing to participate in the trial or withdrawing from the trial at any time will not have any adverse consequences, particularly with regard to their medical care. Participants will also be informed that they may request further information at any time.

Study participants will be informed of the purpose and scope of the collection and use of personal data and, in particular, of the confidentiality obligations of all persons who have access to data that can be used to identify trial subjects as part of the clinical trial. Study participants will also be informed of the data protection measures in accordance with the EU General Data Protection Regulation.

4.9 Exclusivity of study participation

The required exclusive participation in the present study during the intervention and observation period will be ensured by verbal and written information at the initial examination (t1). An appropriate section with a tick box will be added to the informed consent form.

The exclusivity of study participation refers to the exclusion of participation

- in other interventional clinical studies in the period from 4 weeks before the initial examination (t1, day 1) to the time of the last follow-up examination (t4, day 180), and
- participated in therapeutic weight loss programs within the period of the clinical trial (t1-t4) and less than 8 weeks before the entry examination (t1, day 1).

5 Methods: Allocation to the intervention groups

5.1 Randomization

Randomization is carried out using an open source add-in for Microsoft Excel (Kraus, 2014). Age and gender are to be used as stratification factors. The Kullback-Leibler divergence method is to be used as the allocation method (Endo et al., 2006). Randomization and stratification are performed by a biometrician who is not involved in the recruitment of study participants. The necessary stratification factors are blinded to the staff performing the group allocation.

5.2 Blinding

Due to the nature of the planned study (nature-based therapy vs. non-intervention), it is not possible to blind the study participants and investigators to group allocation. However, the group allocation will be blinded to the biometrician conducting the study in order to ensure independent data analysis.

6 Methods: Data collection, management and analysis

6.1 Data collection

Data collection takes place at four time points: Day 1 (t1), day 35 (t2), day 70 (t3) and day 180 (see also chapter 4.5 Study timeline).

The data collection process at time points t1, t2 and t3 is almost identical. The data collection on day 180 is carried out as an online questionnaire survey. It should be noted that some data is collected only once, e.g: socio-demographics (t1), satisfaction with the intervention (t2).

As part of the initial examination (t1), all study participants will undergo a clinical assessment with the study physician on duty, who will decide whether or not the participant is eligible to participate in the study.

Data will be collected by qualified staff of the Institute of Ecomedicine at the Paracelsus Medical University and the University Clinic for Internal Medicine I at the University Hospital of Salzburg according to the following data collection plan:

- T-1 (as soon as there is a positive vote from the Ethics Committee): recruitment, randomization
- T1 resp. day 1: baseline examination
- T2 resp. day 35: examination after guided intervention
- T3 resp. day 70: follow-up examination 1
- T4 resp. day 180: follow-up examination 2

Digital data entry will be performed in a secure REDCap⁵ database system, which will be set up for the NATURE-MET-S study to securely store and process pseudonymized data. REDCap is a secure web application for building and managing online surveys and databases.

In addition, the participants will evaluate the individual therapy sessions using the Mycap mobile app⁶. The following data will be collected:

- Intervention location
- Date, time
- Connectedness to nature
- Individual or group setting
- Details of travel to the intervention location
- Self-assessed physical activity
- Photo of the surroudings (no persons!)
- Affective States (I-PANAS-SF, Perceived Restorativeness Scale (PRS))

MyCap is a freely available participant-facing mobile application that can be installed on iOS and Android devices to capture patient-reported outcomes for any REDCap project.

⁵ REDCap (project-redcap.org)

⁶ https://projectmycap.org/

MyCap's integration with REDCap provides a comprehensive data collection ecosystem and is best suited for longitudinal studies with frequent requests for information from participants (Harris et al., 2022).

All data completed on a participant's device are automatically and immediately synchronized to REDCap. If data are completed while participants are offline, data are synchronized when internet connect is restored and the App is opened.

These are the additional security features of MyCap:

- Participant data is stored locally on the device in an AES-256+SHA2 encrypted database. Data remains on the device if an internet connection is not available. Applies to both iOS and Android devices.
- When an internet connection is available, data is transmitted directly to REDCap using an SSL (TLS v1.2) connection. A hash-based message authentication code (HMAC) is used to verify the integrity of the data and to authenticate the sender.
- 3. Participant entered data (i.e., task responses) are not stored or sent anywhere else. Data exists on the participant's device or on the server.
- 4. Data is wiped from the device after the Mycap App verifies that data has been successfully transmitted. Note that there is an optional MyCap feature that lets a participant see some of the data s/he has entered for an individual task/instrument/survey. By default, data is wiped.
- 5. Participants create a 6-digit PIN that is used to open the App. A participant can disable the PIN feature.

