 - i. What possible positive and negative emotions are induced by exposure to nature?
 - ii. How was the natural exposure carried out (alone/group, public transport)?
 - iii. iii) Where did the natural exposure take place?
 - b. the whole nature-based intervention Secondary Outcome
 - i. Quantitative and qualitative via interviews

The parameters listed under point 3.a are collected using MyCap mobile app³.

³ https://projectmycap.org/

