4.3 Intervention

Nature-based therapy (NBT) consists of the components green exercise/hiking and nature-based mindfulness training.

The hikes are designed to accommodate individuals with varying levels of fitness. Each hike lasts between 1.5 and 2 hours. Participants will traverse distances between 3 and 6 kilometers and ascend to elevations of up to 300 meters on the Salzburg city mountains. A heart rate monitor (wristwatch) will be provided to each participant, which will be calibrated to their specific gender, age, height, and weight. This monitor will be used throughout the intervention. It is recommended that participants complete the hikes within the range of 60-70% of their maximum heart rate (Steele et al., 2021). Additionally, it is advised that training be conducted at a medium level of exertion on the Borg scale (12-16) (Borg, 1982; Löllgen, 2004). A guided group is limited to a maximum of 15 participants and is accompanied by a hiking guide and a mindfulness trainer.

Mindfulness training is based on concentrative movement therapy (Stolze & Badura-MacLean, 2002), a body psychotherapy method that combines physical movements and concentration to promote awareness and mindfulness of one's own body. The objectives of this form of mindfulness training are threefold: firstly, to enhance body awareness through targeted movement exercises; secondly, to reduce stress and promote general well-being; and thirdly, to cultivate mindfulness by training individuals to focus their attention on the present moment.

Intervention group (Nature group) :

Week 1 (day 0 - day 7): Onboarding

- a. 3 x 1,5-2h Green Exercise (guided hikes on the Salzburg city mountains,
 3-6 km each, 100-300 hm, max. 15 people per group)
- b. Within these hikes, participants will receive 20 minutes of nature-based mindfulness training under the guidance of a therapist in a pre-selected restorative and safe location. It is important to note that participants will learn mindfulness training during the process so that they can continue to practice it independently.
- c. It is required that all participants engage in the guided hikes during the initial week of the program.

Week 2 – Week 5 (day 8 – day 35): Integration

- a. 3 x 1,5-2h Green Exercise per week (guided or self-guided hikes (participants can choose) on the Salzburg city mountains, 3-6 km each, 100-300 hm)

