- b. During these hikes, participants will engage in 20 minutes of mindfulness training in a natural and safe environment.
- c. In weeks 2-5, participants may elect to embark on the hikes independently or to participate in the guided hikes.

Week 6 – Week 10 (day 36 – day 70): Self-guided

- a. 3 x 1,5-2h self-guided Green Exercise peer week (Hikes close to home according to prepared tour recommendations 3-6 km, 100-300hm)
- b. During these hikes, participants will engage in 20 minutes of mindfulness training in a natural and safe environment.
- c. In weeks 6-10, no further guided hikes will be offered; participants will be encouraged to conduct the sessions independently. During this period, participants will receive notifications to conduct the therapy sessions via the MyCap app. They will also be requested to complete the app-based questionnaire three times a week during the therapy sessions.

In weeks 11-26, participants will no longer receive reminders to complete therapy sessions. Similarly, they will no longer receive active requests to complete the app-based questionnaire.

The tour recommendations are located throughout Salzburg city to prevent repetition and promote self-determination.

The tour offers recommendations for hikes of varying difficulty levels. Following the initial guided hike, participants are classified according to their fitness level. This is achieved by measuring their heart rate during the hike using a heart rate monitor and by assessing their perceived exertion using the Borg scale (Löllgen, 2004).

The therapy sessions are documented at the location of the mindfulness training sessions using the smartphone app *MyCap*. MyCap is a free, mobile, REDCap-based application for study participants that can be installed on iOS and Android devices to collect the results reported by participants for a specific study previously created in REDCap. The integration of MyCap into REDCap provides a comprehensive and secure data collection system, which is particularly well-suited to longitudinal studies that require frequent requests for information from participants (Harris et al., 2022). The questionnaire asks about the current mood (SPANE, PRS), the perceived exertion, whether the therapy session is being conducted in a group or individually, and whether the patient used public transportation to get to the session (see also 4.4 Outcome parameters).

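### Overall satisfaction is asked once, on day 35 of a programme that section 4.3 runs to day 70, so that rating cannot reflect weeks 6-10 as research question 3b requires

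*Protocol*

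**What the plan says.** - **Section 6.1** names satisfaction with the intervention as an example of a one-off measurement: "some data is collected only once, e.g: socio-demographics (t1), satisfaction with the intervention (t2". The same section places t2 on day 35 and describes it as the "examination after guided intervention".
- **Section 4.3** gives the intervention group three phases. Onboarding fills week 1. It is followed by "Week 2 – Week 5 (day 8 – day 35): Integration" and then by "Week 6 – Week 10 (day 36 – day 70): Self-guided". The last phase still has a prescribed content, "3 x 1,5-2h self-guided Green Exercise peer week", with mindfulness training in each hike and app reminders, but "In weeks 6-10, no further guided hikes will be offered".
- **Section 3.2**, research question 3b, makes participants' evaluation of "the whole nature-based intervention" a secondary outcome. It is to be answered quantitatively and by interview, and question 3 as a whole has a window from T1 to T4 (day 180).
- **Section 4.4.2**, part V.3, labels the process evaluation t1-t4. Under "The following parameters are collected from the study participants for process evaluation" it lists satisfaction, willingness to repeat and willingness to recommend, and it adds interviews after the intervention.
- **Section 4.4.1**, part II, lists satisfaction with the individual session among the app items to be completed for each session.
- **Section 4.5** calls weeks 6-10 the first follow-up phase, and section 6.1 calls T3 a follow-up examination.

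**The concern.** An overall rating given on day 35 can describe only what the participant has experienced by then. If question 3b is about the programme as section 4.3 defines it, the rating comes before the phase in which guided hikes are withdrawn and participants continue alone. Section 4.3 gives the aim of the intervention as building activity and mindfulness into everyday life, so an overall rating ought to take in that phase.

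A rating that is not collected on day 70 cannot be recovered by any later analysis. Staff who follow section 6.1 literally would not ask the item at T3.

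**Working it through.** The protocol gives no figure of its own for this point, so there is nothing to reproduce. The check is schedule arithmetic followed by a comparison of sections.

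**Inputs**
- Single satisfaction rating: t2, day 35 (section 6.1).
- Programme in the intervention group: weeks 1-10, ending on day 70 (section 4.3).
- Frequency: 3 sessions per week in every phase (section 4.3).

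**Arithmetic**
- Elapsed share at t2: 35 / 70 days = 50%, or 5 / 10 weeks.
- Sessions scheduled by t2: 3 × 5 = 15.
- Sessions scheduled in total: 3 × 10 = 30.
- Sessions after t2: 30 − 15 = 15, which is 15 / 30 = 50%. All 15 belong to the self-guided phase.

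**What evaluates weeks 6-10, section by section**

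| Source | Covers weeks 6-10? | Kind of evaluation |
|---|---|---|
| Global satisfaction item, 6.1 | No, asked once on day 35 | Quantitative, overall |
| Session satisfaction in the app, 4.4.1 part II | Yes, if collected | Quantitative, per session |
| Interviews, 4.4.2 part V.3 | Yes, held after the intervention | Qualitative |
| Willingness to repeat and to recommend, 4.4.2 part V.3 | Not determined; only the t1-t4 label applies | Overall |

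The second row is less secure than it looks. Section 4.3 asks participants to complete the app questionnaire three times a week in weeks 6-10, which would give up to 15 session ratings per person. However, the app data list in section 6.1 omits session satisfaction, and so does the description of the questionnaire in section 4.3.

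**Where the sections do not agree**
- Timing of the item: once at t2 (6.1), against membership of a process evaluation labelled t1-t4 (4.4.2).
- Status of weeks 6-10: an intervention phase (4.3), against follow-up (4.5, and the name of T3 in 6.1).

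**The case against.** Four arguments count against a stronger reading.

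1. **A reader might infer that half of the programme goes unrated.** The documents do not support that. Section 4.4.1 asks for satisfaction with each session, section 4.3 keeps the app questionnaire running through week 10, and interviews follow the intervention. The gap is confined to the overall quantitative rating. Still, the session item belongs to question 3a on individual sessions and does not replace a judgement of the whole programme.

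2. **A reader might infer that the t1-t4 label is impossible, because no session has taken place at t1.** The protocol also uses such labels for periods: the per-session app ratings carry the same label, and question 3 has a T1-T4 window. Read as a window, the label can contain a t2 item. Read as a list of visits, it conflicts with section 6.1. The text does not settle which is meant, so this is an ambiguity to resolve and not a proven error.

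3. **Day 35 is the midpoint only under section 4.3.** If weeks 6-10 are follow-up, as sections 4.5 and 6.1 suggest, t2 is a natural point for an end-of-delivery rating. This has weight. But section 4.3 prescribes sessions to day 70 under the intervention group's programme, so one set of sections has to change either way.

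4. **A reader might infer that the t2 rating will be favourable because guides are still provided.** Nothing in the protocol shows this. Participants may also choose to hike on their own in weeks 2-5, so the t2 rating is not purely a rating of guided hikes.

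**Conclusion.** The point holds in a limited form. With section 6.1 followed as written and the programme taken from section 4.3, the single global satisfaction rating comes when 15 of 30 scheduled sessions remain. It cannot reflect any of the self-guided phase, and so does not supply an overall quantitative rating of the whole intervention for question 3b. Per-session app ratings and interviews cover part of the gap, with the app item listed inconsistently.

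This rests on two assumptions: that section 6.1, which names the item, its frequency and the visit, governs over the general label in section 4.4.2; and that weeks 6-10 are part of the intervention. The protocol contradicts itself on the second, which is itself a reason to revise the text.

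The issue is minor. It concerns one item of a secondary process evaluation and leaves the SF-12 and Allostatic Load Index endpoints, power and error rates unaffected. It is worth acting on because the missing rating cannot be obtained afterwards.

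**What to change.** - In section 6.1, collect the global satisfaction item in the intervention arm at T3 as well as at T2.
- In sections 3.2 and 4.4.2, name the T3 rating as the quantitative measure for question 3b and the T2 rating as interim. Replace the t1-t4 label for this item with the time points actually used, and state the time points for willingness to repeat and to recommend.
- Reconcile sections 4.3, 4.5 and 6.1 on whether weeks 6-10 are an intervention phase or follow-up.
- Bring the app lists in sections 4.3 and 6.1 into line with section 4.4.1 on session satisfaction.

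The cost is a few questionnaire items at T3, an on-site visit that already takes place, plus wording changes. No other endpoint or sample size figure has to change.

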6.2 Data management

The REDCap database is used for digital data collection. Each study participant will be assigned a six-digit identification number (ID) for anonymization purposes. Personal data will only be stored in ID-encrypted form. The password-protected master list, which contains the assignment of IDs to personal data, ensures that personal data can be deleted when the study is completed. The master list is stored on a secure data server at the Paracelsus Medical University of Salzburg and is only accessible to the researcher responsible for recruitment, eligibility checks and allocation. Data from medical examinations and surveys are stored in spreadsheet files. Only authorized researchers have access to the data. Participants can access their personal data after completion of the study.

Written consent will be obtained from all study participants for the use of their personal data. The consent forms will include a specific clause on the protection of personal data, informing study participants of how their data will be handled and stored, the purpose of the research, the contact details of the data protection officer and their rights.

All personal data will be handled as defined in General Data Protection Regulation (EU 2016/679), and Finnish Data Protection Act 1050/2018.

Each person involved in the conduct of the study (hiking guides, assistants, etc.) will sign a confidentiality agreement before the start of the study, which will be countersigned by the principal investigator of the study. Confidentiality refers to all circumstances that become known through participation in the study, in particular information about study participants, employees and other cooperation partners regarding economic, operational, technical, tax and personal circumstances as well as internal matters of any kind.

The data will be used for scientific purposes and for possible publication in scientific journals and conferences. In addition, the results of the study will be used for the further development and implementation of effective, sustainable and cost-effective nature-based therapies (including health equity, nature conservation and health economics aspects).

Saliva samples from the Padua (NATURE-MET-P) and Barcelona (NATURE-MET-B) studies will be sent to the Paracelsus Medical University for analysis. The probes will only be labelled with an identification number (ID), so the analysis will be completely anonymous and experimenter-blinded.

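### Randomisation is scheduled at T-1, before the T1 consent review, eligibility decision and baseline, and nothing conceals the allocation until T1 is complete

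*Protocol*

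**What the plan says.** The data collection plan in Protocol 6.1 puts "recruitment, randomization" at T-1, a stage that opens once the ethics committee has approved the study. The next entry, T1 (day 1), is the "baseline examination". The same section says that at T1 "all study participants will undergo a clinical assessment with the study physician on duty, who will decide whether or not the participant is eligible". According to 4.8, the criteria and the consent form "will be sent to participants in advance and will be reviewed at the inclusion visit (t1"). Section 4.5 describes T1 as "Baseline data assessment directly before the intervention for intervention and control group", which fits groups that already exist at that visit. Before T1, 4.7 provides only an online registration questionnaire with a first check of the criteria.

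On roles, 5.1 states: "Randomization and stratification are performed by a biometrician who is not involved in the recruitment of study participants". It then refers separately to staff who carry out the allocation and who do not see the stratification factors. Section 6.2 says that the list linking IDs to persons "is only accessible to the researcher responsible for recruitment, eligibility checks and allocation".

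Section 5.2 says that participants and investigators cannot be blinded. Sections 3.3 and 6.3 promise an intention-to-treat analysis.

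**The concern.** Randomisation makes the arms comparable only if the people who enter are settled without regard to their arm. Here the decision on who enters comes after allocation. A participant who learns of a waiting-list place may decline at T1. A participant assigned to hiking may be judged unfit for hikes when the same person in the control arm would have been accepted. Someone who already knows the arm may answer the baseline SF-12 differently.

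Each of these would make the analysed groups differ from the randomised groups, or distort a baseline from which change in a primary outcome is measured. A larger sample does not remove such a bias, and later modelling does not reliably remove it.

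**Working it through.** The point concerns the order of events, so there is no figure in the plan to reproduce. The sections are compared instead.

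**1. Order.**
- T-1: recruitment and randomisation (6.1), with an online first screen at registration (4.7).
- T1, day 1: criteria and consent reviewed (4.8), physician decides eligibility (6.1), baseline measured (4.5, 6.1).
- Then the intervention (4.5).

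People are thus randomised on an online screen, and the decisive check follows.

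**2. Could the arm be known at T1?** Section 5.2 leaves participants and investigators unblinded, and no section holds the allocation back. Section 4.3 counts week 1 from day 0 to day 7 and requires three guided hikes in it, in groups of at most 15. With T1 on day 1, those groups must be formed at about T1. Knowledge of the arm at T1 is therefore likely, but it is an inference. The protocol does not state when the allocation is disclosed.

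**3. Could the T1 steps respond to the arm?** Several criteria in 4.2 rest on judgement (orthopaedic illness that rules out hiking, uncontrolled metabolic disease) or on self-report (IPAQ-SF category, WHO-5 score, nature use). The participant can also withdraw at any time (7.1). The SF-12 is self-reported and is a primary outcome (4.4.1).

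**4. What happens to those lost at T1?** No section says. A person randomised at T-1 but excluded or absent at T1 has no baseline, so the carry-forward rule in 6.3 has nothing to carry forward. Such people would probably disappear from the analysis.

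**5. Scale, on assumptions only.** The protocol gives no rate of failure or refusal at T1. At an assumed 5% to 20%: 0.05 × 140 = 7 and 0.20 × 140 = 28 people.

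As a side check on precision, suppose this loss x comes on top of the planned 40% drop-out. Completers per arm are then 70 × (1 − x) × 0.60. Power is interpolated linearly in the table in 4.6, read as per arm.

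| x | Completers per arm | Power |
|---|---|---|
| 0 | 42.0 | 0.828 |
| 0.05 | 39.9 | 0.816 |
| 0.10 | 37.8 | 0.788 |
| 0.20 | 33.6 | 0.732 |

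For example, at x = 0.10: 0.684 + 0.78 × (0.817 − 0.684) = 0.788. This shows lost precision only. It does not measure bias.

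**The case against.** The strongest reply is that the protocol does not say anyone learns the arm before T1, and that it contains some separation of duties. Section 4.7 gives clinical inclusion to the hospital clinic and the intervention to the Institute, and the online screen should remove some ineligible people early. This is fair, but neither arrangement is a concealment safeguard. A biometrician who stands apart from recruitment protects how the allocation is generated, not an eligibility decision made after it.

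Five stronger readings are tempting and are not supported:

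- *The arm is known at T1.* This is inferred from the open design and the timetable. It is not stated.
- *Consent is signed only after randomisation.* Section 4.8 says that the documents are sent ahead and reviewed at T1. It does not rule out a signature before T-1.
- *Section 6.2 contradicts 5.1.* Section 5.1 gives the biometrician randomisation and stratification, and itself mentions other staff who carry out the allocation. The researcher in 6.2 may be one of them. Joining eligibility checks and allocation in one role is a weakness, not a clear contradiction.
- *Intention-to-treat cannot be met.* It can, if everyone is analysed as randomised and T1 exclusions are reported by arm. The order endangers it.
- *The bias is 1 to 2 SF-12 points.* If the lowest-scoring fraction q leaves one arm only, that arm's mean rises by φ(z_q)/(1 − q), where φ is the normal density and z_q the q-quantile: 0.109 SD at q = 0.05 and 0.195 SD at q = 0.10. That is 1.1 and 1.95 points at an assumed SD of 10. But this is a shift in level, whereas the 2.5-point threshold in 4.4.1 concerns change and 6.3 tests the group-by-time interaction. With loss by lowest baseline score and an assumed baseline to follow-up correlation r, change shifts by (r − 1) times the level shift: −0.5 to −1.0 points at r = 0.5, and −0.3 to −0.6 at r = 0.7. The effect is smaller and in the opposite direction, and SD, r and q are all assumed.

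The reply therefore limits how far the point goes but leaves the order of events and the missing concealment untouched.

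**Conclusion.** The concern holds as a point about sequence and concealment. As written, the plan randomises first and settles eligibility, consent review and baseline afterwards, in an open trial with no stated concealment. Selection after randomisation and an SF-12 baseline influenced by the arm are real risks of following it. The size and direction of any bias cannot be derived from the document, and the case does not rest on a number.

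It rests on the T-1 and T1 entries in 6.1 meaning what they say, and on the inference that the arm can be known at T1. If actual practice already completes T1 before allocation, 6.1 misstates it and still needs correcting. A separate analysis plan could define how exclusions are counted, but it cannot change an order of conduct that the protocol sets.

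**What to change.** - **6.1:** change the order to signed consent, T1 eligibility decision and completed baseline, then randomisation, then the first hike. The biometrician releases the allocation only after T1 is complete. This can be done by batch within each of the two rounds, since age and gender are the only stratification factors (5.1).
- **6.2:** separate allocation from recruitment and eligibility checks. If allocation there means something else, such as assigning IDs, say so.
- **5.1:** state who the staff carrying out the allocation are and what they do.
- **3.3 and 6.3:** analyse all randomised participants, and report any exclusion after randomisation by arm with the reason.

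If logistics force randomisation before T1, the weaker alternative is to have eligibility confirmed and the baseline taken by someone unaware of the allocation. That does not stop a participant who knows the arm from declining or answering differently.

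The cost is a protocol amendment and a short gap between T1 and the first hike to form the guided groups. Section 4.5 places T1 directly before the intervention and 4.3 counts week 1 from day 0, so these sections must be reconciled with the gap and the day 1, 35, 70 and 180 anchors stated accordingly. No additional participants or examinations are needed.
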